5.6 Duration of Follow Up

After completion of protocol therapy or removal from protocol therapy, participants will be followed for 3 years, or until death, whichever occurs first. Follow-up studies should be done annually at 12, 24, and 36 months after therapy (see Table 2 for scheduled tests).

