⁶ End of treatment disease assessment imaging window +/- 14 days from day 28 of Cycle 6.

⁷ All Follow-Up Assessments to be performed 12, 24, and 36 months from the off-treatment date (i.e. Day 28 of last administered cycle) +/- 31 days.

⁸ 12, 24, and 36 months after completion of therapy (i.e. Day 28 of last administered cycle)

CONFIDENTIAL

This document is confidential. Do not disclose or use except as authorized.

9 CRITERIA FOR RESPONSE – STRATUM 1

In contrast to leukemia or other malignancies the terms “remission” or “relapse” should be avoided. In accordance with the nature of Histiocytosis the following definitions should be applied to judge the effect of treatment. The response criteria stated below has been designed by the Histiocyte Society to be applied in therapeutic studies of LCH and should be used for therapeutic decisions.⁶⁸

Table 3: Definition of Disease State

Main Category	Sub-categories	Definition
Non-active Disease (NAD)		Resolution of all signs/symptoms (no evidence of disease)
Active Disease (AD)	Regressive Disease (Better)	Regression of signs/symptoms, and no new lesions.
	Stable Disease (Stable)	Persistence of signs or symptoms, and no new lesions.
	Progressive Disease* (Worse)	Progression of signs/symptoms and/or appearance of new lesions.

* Progression of skeletal lesions is defined as unequivocal enlargement of the size of existing lesions and/or appearance of new lesions.

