13.3 Study Design/Endpoints

The primary endpoint within each stratum will be the proportion of responders. A responder is defined as an eligible, evaluable participant who achieves either complete resolution or regression of disease, i.e., their disease gets "Better" per section 9.1, as the best overall response at any time up to and including the End of Cycle 2 assessment, which must be completed on Day 28 of Cycle 2 +/- 7 days, and must be completed prior to starting Cycle 3.

Secondary endpoints are:

- a) Progression-free survival (PFS), where time to event for PFS is the time from study enrollment until the time of first occurrence of new lesions, progressive disease, or death from any cause, or until last contact if no event occurs;
- b) Overall survival (OS), calculated as the time from enrollment until death or last contact;

CONFIDENTIAL

This document is confidential. Do not disclose or use except as authorized.

- c) Feasibility, which is assessed by the proportion of patients who experience a toxicity-event. Participants who have clofarabine stopped because of toxicity concerns will be considered to have experienced a toxicity-event. Otherwise, participants who complete therapy or who are removed from protocol therapy for reasons related to disease progression, second malignancy or death unrelated to protocol therapy will be considered to have successfully tolerated treatment; and,
- d) The proportion of participants reporting grades 3-4 toxicity, for each CTCAE v4.0 toxicity code.

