13.6 Statistical Methods to Address Objectives

Objective 1.3 - Monitoring Rule A will be used to address primary objective 1.3. The analysis will include all evaluable Stratum 1 participants. In addition, a 95% confidence interval will be placed on the response rate.

Secondary Objective 1.4.a – Descriptive analyses using the methods of Kaplan and Meier (with standard errors per Peto) will be performed to calculate the PFS and OS within each stratum and overall. Lifetables will also be constructed.

Secondary Objective 1.4.b – Monitoring Rule B will be used to address secondary objectives 1.4.b and 1.4.c. In addition, a descriptive tabulation of the proportion of participants reporting grade 3 and higher toxicity, separately by stratum (1 and 2) and by CTC toxicity code, will be generated for all evaluable patients. A given participant will be counted only one time per toxicity code at the maximum grade regardless of the number of times that participant experienced the toxicity.

Secondary Objective 1.4.c – Within Stratum 2 and within subgroups of Stratum 2, we will calculate the proportion of evaluable patients who are responders, and place 95% confidence intervals on these proportions. A descriptive tabulation of the proportion of participants reporting grade 3 and higher toxicity, by CTC toxicity code, will be generated for Stratum 2 patients. A given participant will be counted only one time per toxicity code at the maximum grade regardless of the number of times that participant experienced the toxicity.

CONFIDENTIAL

This document is confidential. Do not disclose or use except as authorized.

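### Annual post-treatment scans with ordinary Kaplan-Meier PFS date scan-found progressions up to about 12 months late, at times that depend on cycles received

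*Combined protocol and SAP*

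**What the plan says.** **Endpoint.** Section 13.3 starts the clock at enrolment: "time to event for PFS is the time from study enrollment until the time of first occurrence of new lesions, progressive disease, or death". It gives no rule for dating a progression first seen at a scheduled scan.

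**Method.** Section 13.6 says: "Descriptive analyses using the methods of Kaplan and Meier (with standard errors per Peto) will be performed to calculate the PFS and OS". Curves are planned within each stratum and overall. The plan has no interval-censored estimate and no sensitivity analysis for assessment timing.

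**Assessment times.** In Table 2 (section 8), scheduled disease assessment after baseline is marked at End of Cycle 2, at end of treatment (imaging dated from Day 28 of Cycle 6) and at follow-up. Footnote 7 sets follow-up: "All Follow-Up Assessments to be performed 12, 24, and 36 months from the off-treatment date (i.e. Day 28 of last administered cycle", with a window of 31 days either side. Footnote 8, attached to disease assessment and skeletal survey, uses the same anchor: "12, 24, and 36 months after completion of therapy (i.e. Day 28 of last administered cycle". Section 5.6 agrees: "Follow-up studies should be done annually at 12, 24, and 36 months after therapy". Its follow-up period also starts when therapy ends: "participants will be followed for 3 years, or until death, whichever occurs first". Table 2 gives no imaging date for participants who stop before Cycle 6.

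**Treatment length.** Section 5 allows at most 6 cycles of 28 days, each extendable to day 42.

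**The concern.** Kaplan-Meier treats the recorded date as the event date. A progression that begins between two scans, without symptoms, can be recorded only at the next scan. After treatment the scans are a year apart, so the recorded date can be about a year late and the curve stays flat between scans.

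The scan times also differ between participants. The clock runs from enrolment, but the annual visits run from the end of treatment, and only participants who reach Cycle 6 have a dated end-of-treatment scan. Two people with the same disease course can therefore have different PFS times because they received different numbers of cycles or had different delays.

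Estimating PFS is the first secondary objective (section 1.4). In a single-arm trial, a PFS percentage or median is likely to be read against other series. If it was taken inside an assessment gap, it partly reflects the calendar.

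**Working it through.** **The plan's own figure.** The documents give no PFS rate, median or event count. The only efficacy design figure is Rule A in section 13.5. The probability of a positive result is the sum over x = 8 to 13 of P(Bin(13, p) = x) × P(Bin(7, p) ≥ 14 − x). This gives 0.0932 at p = 0.53 and 0.908 at p = 0.80, matching the stated alpha of 0.093 and power of 91%. Rule A uses response up to End of Cycle 2, so nothing below touches it.

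**Calendar.** Off-treatment day = (cycles − 1) × cycle length + 28, with 30.44 days to a month and therapy assumed to start at enrolment.

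| Participant | Off-treatment day | Scheduled scans, months from enrolment |
|---|---|---|
| 2 cycles | 28 + 28 = 56 | 1.8, 13.8, 25.8, 37.8 |
| 6 cycles, undelayed | 5 × 28 + 28 = 168 | 1.8, 5.5, 17.5, 29.5, 41.5 |
| 6 cycles, all delayed to day 42 | 5 × 42 + 28 = 238 | 2.3, 7.8, 19.8, 31.8, 43.8 |

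The first annual scan moves by 17.5 − 13.8 = 3.7 months between 2 and 6 undelayed cycles. With maximum delay it moves by 19.8 − 13.8 = 6.0 months. Both are before the 31-day window.

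**Expected curve.** Let S(t) = 0.5^(t/m) be true PFS with median m, the same for everyone. Let a(t) be the last scheduled scan at or before t. Let c be the share of progressions found clinically at onset. Then expected Kaplan-Meier PFS is c × S(t) + (1 − c) × S(a(t)). The documents give neither m nor c, so both are assumptions.

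For m = 12 at 12 months, S = 0.50:
- 6 cycles, c = 0: 0.5^(5.52/12) = 0.73.
- 2 cycles, c = 0: 0.5^(1.84/12) = 0.90.
- c = 0.5: (0.50 + 0.727)/2 = 0.61 and (0.50 + 0.899)/2 = 0.70.

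For m = 12 at 15 months, S = 0.42:
- 2 cycles, c = 0: 0.5^(13.84/12) = 0.45.
- 6 cycles, c = 0: still 0.73.
- c = 0.5: 0.44 (2 cycles) and 0.57 (6 cycles).

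**Range over m** (each cell: 2 cycles / 6 undelayed cycles):

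| m (months) | 12-month true | c = 0 | c = 0.5 | 15-month true | c = 0 | c = 0.5 |
|---|---|---|---|---|---|---|
| 6 | 0.25 | 0.81 / 0.53 | 0.53 / 0.39 | 0.18 | 0.20 / 0.53 | 0.19 / 0.35 |
| 12 | 0.50 | 0.90 / 0.73 | 0.70 / 0.61 | 0.42 | 0.45 / 0.73 | 0.44 / 0.57 |
| 24 | 0.71 | 0.95 / 0.85 | 0.83 / 0.78 | 0.65 | 0.67 / 0.85 | 0.66 / 0.75 |

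**Pooled curve.** Section 13.6 plans no curve by cycles received, so the groups must be mixed. As an illustration, let 24% stop after Cycle 2 without progression. This is 6 of 25, the most toxicity-events that Stage 3 of Rule B accepts. With m = 12 and c = 0, 12-month PFS reads 0.24 × 0.899 + 0.76 × 0.727 = 0.77. With c = 0.5 it reads 0.24 × 0.70 + 0.76 × 0.614 = 0.64. The true value is 0.50.

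**Latest annual scans.** Maximum delay plus the window gives 19.8 + 1.0 = 20.8 and 31.8 + 1.0 = 32.8 months.

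**The case against.** **The off-treatment anchor is not the whole cause.** At 12 months neither modelled group has reached an annual visit. The contrast of 0.73 with 0.90 comes from the Cycle 6 scan, and the distance from 0.50 comes from the long gap. Annual scans at 6, 18 and 30 months from enrolment for everyone would still give 0.5^(6/12) = 0.71 at 12 months. This stands. The anchor acts only once annual scans begin, as at 15 months.

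**Early stoppers do not always look better.** A reader might infer that they do from the 12-month values. The 15-month values go the other way, so the documents support dependence on the schedule but no constant direction.

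**Detection dating is inferred.** Section 13.3 speaks of "time from study enrollment until the time of first occurrence of new lesions, progressive disease, or death from any cause" and does not name the scan date. True, but onset between scans is unobserved, so the assessment date is the only one available for these events. The missing rule is itself the gap.

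**Much progression will surface clinically.** Table 3 counts signs and symptoms, and section 5.2 requires an examination and no progression before each cycle. Zero clinical detection is therefore an extreme case. The effect shrinks with c but remains at c = 0.5. Table 2 marks no physical examination in the follow-up column, so planned clinical detection is weakest in the annual gaps.

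**PFS is descriptive, and the sample is small.** At n = 20 a 95% interval around 0.50 is about 1.96 × √(0.25/20) = ±0.22. The pooled shift of 0.64 − 0.50 = 0.14 at c = 0.5 lies inside it. This limits the weight of the point. However, the shift is systematic, and the Kaplan-Meier standard error does not reflect it.

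**Conclusion.** The concern holds as late dating of scan-found progressions combined with dependence on each participant's schedule. In the two main schedules the delay can reach about 12 months on nominal dates. With an assumed true median of 12 months, 12-month Kaplan-Meier PFS is overstated by 0.23 to 0.40 if all progression is scan-detected (0.73 or 0.90 against 0.50). The overstatement is 0.11 to 0.20 if half is found clinically (0.61 or 0.70). These sizes rest on exponential progression common to all, exact adherence to the calendar and therapy starting at enrolment.

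A reader might also infer that the median PFS can fall only on a visit date. That would need every event to be scan-detected. Deaths and clinically found progressions carry their own dates and are unaffected. The primary response rule is unaffected too. This is a low-cost improvement to a descriptive secondary analysis and does not challenge the trial's main conclusion.

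**What to change.** - **Section 13.3:** state that progression found at an assessment is dated to that assessment, and that the last progression-free assessment is recorded with it.
- **Section 13.6:** add an interval-censored (Turnbull) PFS estimate, with exact dates for deaths and clinically dated progressions. Report it alongside the Kaplan-Meier curve, with assessment times marked on the curve.
- **Reporting:** do not quote Kaplan-Meier PFS inside the 12-month gaps without that estimate. Place any landmark after the latest possible annual scan, at about 21 and 33 months from enrolment.

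A late landmark is not enough alone. At 21 months a 2-cycle participant is still 21 − 13.8 = 7.2 months past the last scan, so the interval-censored estimate is needed there too.

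The change needs wording and a standard routine applied to assessment dates that the calendar already generates, with no added visits. The downside is wider, stepped estimates at 20 to 25 participants, undetermined within intervals where nobody was assessed.

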9.1 Definition of Response Criteria

Table 4: Three Categories of Response

Response Category	Definition
Better	
 Complete disease resolution (NAD) Regression (AD better)
Intermediate	
 Stable (unchanged)
Worse	
 Progression*

* Progression of skeletal lesions is defined as unequivocal enlargement of the size of existing lesions and/or appearance of new lesions. In patients with risk organ involvement the overall response (and hence therapeutic decision) depends on response in risk organs.

9.2 CRITERIA FOR RESPONSE – STRATUM 2

For PET-based assessments, a clinical response of progressive metabolic disease (PMD), no metabolic response (NMR), partial metabolic response (PMR), or complete metabolic response (CMR) will be determined. PMD/PD includes radiological evidence of progression per Lugano Classification Revised Staging System for malignant lymphoma⁶⁹. The PET scan metabolic uptake will be graded using the Deauville 5-point scale, with a score of ≤ 3 considered to represent a CMR.

Deauville 5-point scale: 1 = no uptake above background; 2 = uptake \leq mediastinum; 3 = uptake $>$ mediastinum but \leq liver; 4 = uptake moderately $>$ liver; 5 = uptake markedly higher than liver and/or new lesions; X = new areas of uptake unlikely to be related to lymphoma.

CONFIDENTIAL

This document is confidential. Do not disclose or use except as authorized.

Table 5: CMR / CR

Response/Site	FDG PET-CT-Based (Complete Metabolic Response)	CT-Based (CR) ^a All of the following:
Lymph nodes and extralymphatic sites	Score 1, 2 or 3 with or without a residual mass on 5-Point-Scale. It is recognized that in Waldeyer's ring or extranodal sites with high physiologic uptake or with activation within spleen or marrow (eg, with chemotherapy or myeloid colony-stimulating factors), uptake may be greater than normal mediastinum and/or liver. In this circumstance, complete metabolic response may be inferred if uptake at sites of initial involvement is no greater than surrounding normal tissue even if the tissue has high physiologic uptake.	Target nodes/nodal masses must regress to ≤ 1.5 cm in LDi No extra lymphatic sites of disease
Non-measured lesion	Not applicable	Absent
Organ enlargement	Not applicable	Regress to normal
New lesions	None	None
Bone marrow ^b	No evidence of FDG-avid disease in marrow	Normal by morphology; if indeterminate, IHC negative

^a CT-Based could also apply to MRI-based

^b Only if bone marrow involvement at diagnosis

Table 6: PMR / PR

Response/Site	FDG PET-CT-Based (Complete Metabolic Response)	CT-Based (CR) ^a All of the following:
Target nodes/nodal masses, extranodal lesions	Score 4 or 5 with reduced uptake compared with baseline and residual mass(es) of any size At interim, these findings suggest responding disease At end of treatment, these findings suggest residual disease	≥ 50% decrease in SPD of up to 6 target measurable nodes and extranodal sites When a lesion is too small to measure on CT, assign 5mm X 5mm as the default value; when no longer visible, 0 X 0mm; for a node > 5mm X 5mm, but smaller than normal, use actual measurement for calculation
Non-measured lesion	Not applicable	Absent/normal, regressed, but no increase
Organ enlargement	Not applicable	Spleen must have regressed by >50% in length beyond normal
New lesions	None	None
Bone marrow ^b	Residual uptake higher than uptake in normal marrow but reduced compared with baseline (diffuse uptake compatible with reactive changes from chemotherapy allowed). If there are persistent focal changes in the marrow in the context of a nodal response, consideration should be given to further evaluation with MRI or biopsy or an interval scan.	Not applicable

^a CT-Based could also apply to MRI-based

^b Only if bone marrow involvement at diagnosis

Table 7: NMR/ SD

Response/Site	FDG PET-CT-Based (Complete Metabolic Response)	CT-Based (CR) ^a All of the following:
Lymph nodes and extralymphatic sites	Score 4 or 5 with no significant change in FDG uptake from baseline at interim or end of treatment	< 50% decrease in SPD of up to 6 target measurable nodes and extranodal sites; no criteria for Progressive Disease met
Non-measured lesion	Not applicable	No increase consistent with Progression
Organ enlargement	Not applicable	No increase consistent with Progression
New lesions	None	None
Bone marrow ^b	No change from baseline	Not applicable

^a CT-Based could also apply to MRI-based

^b Only if bone marrow involvement at diagnosis

Table 8: PMD / PD

Response/Site	FDG PET-CT-Based (Complete Metabolic Response)	CT-Based (CR) ^a All of the following:
Individual target nodes/nodal masses Extranodal lesions	Score 4 or 5 with an increase in intensity of uptake from baseline and/or new FDG-avid foci consistent with lymphoma at interim or end-of-treatment assessment	An individual node/lesion must be abnormal with: LDi > 1.5 cm & Increase by ≥ 50% from PPD nadir & An increase in LDi or SDi from nadir 0.5 cm for lesions ≤ 2cm 1.0 cm for lesions > 2cm In the setting of splenomegaly, the splenic length must increase by > 50% of the extent of its prior increase beyond baseline (eg, a 15cm spleen must increase to 16cm). If no prior splenomegaly, must increase by at least 2cm from baseline. New or recurrent splenomegaly
Non-measured lesion	None	New or clear progression of preexisting nonmeasured lesions
New lesions	New FDG-avid foci consistent with lymphoma rather than another etiology (e.g., infection, inflammation). If uncertain regarding etiology of new lesions, biopsy or interval scan may be considered.	Regrowth of previously resolved lesions A new node > 1.5cm in any axis A new extranodal site > 1.0cm in any axis; if < 1.0 cm in any axis, its presence must be unequivocal and must be attributable to lymphoma. Assessable disease of any size unequivocally attributable to lymphoma.
Bone marrow ^b	New or recurrent FDG-avid foci	New or recurrent involvement

^a CT-Based could also apply to MRI-based

^b Only if bone marrow involvement at diagnosis

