8 STUDY CALENDAR

Baseline laboratory tests are to be conducted within 14 days prior to start of protocol therapy. Other evaluations (scans, pathology, EKG, etc.) must be done within 30 days of study entry. In the event that the participant's condition is deteriorating, laboratory evaluations should be repeated within 48 hours prior to initiation of the next cycle of therapy.

All assessments must be performed prior to administration of any study medication. All study assessments and medications should be administered within ± 3 days of the protocol-specified date, unless otherwise noted.

All follow-up assessments must be performed 12, 24, and 36 months from the off-treatment date (i.e. Day 28 of last administered cycle) ± 31 days.

A calendar for the time points when the required study data should be obtained is provided below.

CONFIDENTIAL

This document is confidential. Do not disclose or use except as authorized.

Table 2: Required Data / Study Calendar

Assessments	Baseline/ Screening (within 14 days)	Before Starting Each Cycle (within 3 days)	During Each Cycle	End of Cycle 2 ⁵	End of Treatment (+/- 7 days from day 28 of Cycle 6)	Follow- up ⁷ (+/- 31 days)
Informed Consent	X ¹					
Medical History Concurrent Condition Concomitant Medications/ Transfusions	X					
Height		X			X	
Weight		X			X	
BSA		X			X	
Physical exam/Vital Signs	X	X			X	
Performance Status	X ¹	X			X	
Hematology (CBC/Diff/Plts)	X ¹	X	Weekly ⁴		X	X ²
Electrolytes including Ca ⁺⁺ , PO ₄ , Mg ⁺⁺	X	X	Weekly ⁴		X	X ²
Creatinine, BUN, Serum glucose	X ¹	X	Weekly ⁴		X	X ²
LFTs (Total Protein/Alb., ALT, AST, ALP, Billi.)	X ¹	X	Weekly ⁴		X	X ²
Uric acid	X	X ²			X ²	
Serum β-HCG ³	X ¹				X	
EKG	X				X ²	
Urinalysis	X	X			X	
Bone Marrow Biopsy, Aspirate and Smear	X ² (within 30 days)			X ²	X ²	X ²
Disease Assessment/ Response Documentation (CT/MRI/ Bone Scan/ PET, as clinically indicated)	X ¹ (within 30 days)			X	X ⁶	X ⁸
Chest X-Ray PA and L	X				X	
Skeletal survey (stratum 1 only)	X			X	X ⁶	X ⁸
Clofarabine Administration			Days 1-5			
Adverse Event Assessment	X	X	Weekly ⁴		X	

¹ Source documents are required for eligibility review before registration.

² As clinically indicated.

³ For females of childbearing potential.

⁴ Weekly assessments are recommended as clinically indicated, to be completed every 7 days, +/- 3 days.

⁵ End of Cycle 2 assessments must be completed on Day 28 of Cycle 2 +/- 7 days, and prior to starting Cycle 3.

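### In Stratum 2 a PET score of 1–3 counts as complete metabolic response with no condition on baseline uptake, so an unchanged mass can be classed as CMR

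*Combined protocol and SAP*

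**What the plan says.** Section 9.2 takes its Stratum 2 response criteria from lymphoma and sets them out in two parallel columns, PET-based and CT-based.

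- **CMR on PET.** The text of 9.2 grades uptake on the Deauville scale, "with a score of ≤ 3 considered to represent a CMR". Table 5 repeats this as "Score 1, 2 or 3 with or without a residual mass on 5-Point-Scale". The column also requires no new lesions and, if marrow was involved at diagnosis, no avid marrow disease. Organ enlargement and non-measured lesions are marked as not applicable.
- **PMR on PET (Table 6).** "Score 4 or 5 with reduced uptake compared with baseline and residual mass(es) of any size".
- **NMR on PET (Table 7).** "Score 4 or 5 with no significant change in FDG uptake from baseline at interim or end of treatment".
- **CR on CT (Table 5).** "Target nodes/nodal masses must regress to ≤ 1.5 cm in LDi", with no extralymphatic disease. In Table 7, a decrease of less than 50% in the summed products without progression is stable disease (SD).

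Table 2 makes a disease assessment mandatory at baseline but leaves the modality open: "CT/MRI/ Bone Scan/ PET, as clinically indicated". Section 3.1 requires active disease, not FDG-avid disease.

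Section 13.3 defines a responder, for both strata, as a participant in the Better category of section 9.1. Table 4 there puts stable, unchanged disease in the Intermediate category. Section 13.4 assigns response according to section 9 as a whole. For Stratum 2 and its subgroups, section 13.6 states that "we will calculate the proportion of evaluable patients who are responders", with 95% confidence intervals.

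**The concern.** A response category should record a change from baseline. The PET route to CMR records only a state after treatment. If the lesion was already at or below liver uptake before the first dose, the state is met without any change. If there was no baseline PET, a true metabolic response and a lesion that was never avid look the same.

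Stratum 2 exists to generate hypotheses about response rates in five rare histologies, from at most 20 participants. With numbers that small, one or two participants classed as CMR by default can change how promising a histology looks. The plan gives the reader of the results no means of seeing that this has happened.

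**Working it through.** **1. Categories open to an unchanged lesion that scored 1–3 at baseline**

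| PET category | Requires | Met? |
|---|---|---|
| CMR | score 1–3, no new lesions, marrow condition if relevant | yes |
| PMR | score 4 or 5, uptake reduced from baseline | no |
| NMR | score 4 or 5, uptake unchanged from baseline | no |
| PMD | score 4 or 5 with rising uptake, new foci, or radiological progression | no |

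CMR is the only PET category left. By the CT column of Table 7, the same unchanged mass is SD.

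**2. Does other text close the gap?**

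- The only reference in the CMR cell to where disease began is the exception for high physiologic uptake: "complete metabolic response may be inferred if uptake at sites of initial involvement is no greater than surrounding normal tissue". It does not require those sites to have been avid.
- The Lugano citation in 9.2 is attached to progression only.
- Section 9.3 asks for response to last 8 weeks. Stable non-avid disease passes that test.
- Nothing in section 9 says which column applies, or what happens when the two disagree.

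**3. The plan's own response figure**

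Stratum 2 has no power statement. The only response design is the Stratum 1 two-stage rule (8 or more of 13, then 14 or more of 20). Its probability of success is the sum over x = 8 to 13 of P(X₁ = x; 13, p) × P(X₂ ≥ 14 − x; 7, p). At p = 0.80 this is 0.9085 (stated 91%). At p = 0.53 it is 0.0932 (stated 0.093). Both reproduce. Stratum 1 does not use section 9.2, so neither figure moves.

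**4. Size in Stratum 2**

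One participant: 1/20 = 5 points overall. If 20 participants split evenly over five histologies, 20/5 = 4 and 1/4 = 25 points.

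Let p be the true response rate and f the share of non-responders classed as CMR by default. The apparent rate is p + f(1 − p). The documents give no avidity rate, so f is an assumption:

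| True rate p | f = 5% | f = 10% | f = 20% | f = 30% |
|---|---|---|---|---|
| 20% | 24% | 28% | 36% | 44% |
| 40% | 43% | 46% | 52% | 58% |

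For example, 0.20 + 0.20 × 0.80 = 0.36.

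An illustration with assumed counts and exact (Clopper-Pearson) intervals, since the plan names no interval method: if 2 of 6 responders in 20 were CMR by default, 6/20 = 30% (11.9% to 54.3%) becomes 4/20 = 20% (5.7% to 43.7%). In a subgroup of 10, removing one moves 3/10 = 30% (6.7% to 65.2%) to 2/10 = 20% (2.5% to 55.6%).

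**The case against.** The strongest reply is that section 13.3 already excludes the error. It counts only the Better category of 9.1, and unchanged disease is Intermediate there, so a reader who infers that the plan counts such a participant as a complete responder goes too far. That stands, and it is why the point is that the participant *can be classified* as CMR. It does not remove the problem. Section 9.1 sits under the Stratum 1 criteria, section 13.4 sends the assessor to section 9 including 9.2, and no text maps a 9.2 category to the responder count. The two routes give different answers for the same participant.

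A second reply is that PMR and NMR need a baseline comparison, so the PET column presupposes a baseline PET, and that no sensible site would follow a non-avid lesion by PET. This lowers the likely frequency. But CMR itself can be assigned without a baseline scan, and a presupposition is not a rule. Without a baseline PET a score of 1–3 may also be a genuine response; the difficulty is that the two cases cannot be separated.

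Third, Stratum 2 is exploratory, and its intervals are far wider than a one-participant shift. This also stands and limits the consequence. The shift is nonetheless one-directional: it can only raise the response rate.

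A reader might further infer that a comparison between histologies is distorted, or that errors gather in the least avid one. The documents do not support either: 13.6 plans proportions within groups and no comparison between them, and no avidity data are given for any histology.

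**Conclusion.** The gap is real. As written, 9.2 gives an unchanged lesion with a baseline score of 1–3 no PET category except CMR, while the CT column gives SD and section 13.3 gives no response. This happens only when the PET column is used and there are no new lesions or avid marrow disease.

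The effect is confined to the exploratory Stratum 2 proportions. The arithmetic per participant is firm; the subgroup figure rests on an even split. How many participants would be affected is unknown, and the inflation table shows a range of assumed values, not an estimate. It would be wrong to infer that the trial's main conclusion is at risk, because the Stratum 1 decision rule does not touch these criteria. The change is still worth making, since a short addition removes an avoidable upward bias.

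**What to change.** Add to section 9.2:

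- The PET column applies only to involved sites scored 4 or 5 on a baseline PET.
- Sites that were not avid, or not PET-scanned, at baseline are classified by the CT/MRI column, using the modality that documented them at the mandatory baseline disease assessment.
- An overall CMR/CR requires both groups of sites to meet their criteria.

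The rule has to work by site. Requiring just one avid site per participant would still let unchanged non-avid lesions through.

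In section 13.3, state that a Stratum 2 responder is one with CMR/CR or PMR/PR under 9.2. In 13.6, report Stratum 2 responders by the column used.

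The cost is a few sentences and some constraint on imaging. The same modality must be used at baseline and at the End of Cycle 2 assessment, and Table 2 should say so, because it guarantees CT/MRI no more than PET. A few participants move from PET to CT/MRI criteria, and the Stratum 2 rate may be slightly lower. Lesions that do not suit size measurement, such as the skin nodules of JXG or the bone lesions of ECD, would have to be judged under the non-measured rows of the CT column.
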